Intentions Test and Modified Fatigue Impact Scale. A questionnaire will also be administered to obtain demographic information (age, gender, ethnicity, race, and education level), service-related information (active duty or reserves and period of service time, and Parkinson's disease-related history (year of diagnosis, number of years on Parkinson's medication and side of motor symptom onset), and current general computer use and use of commercially available cognitive training tools.

Table 1: Standardized Assessment Tools for In-Person Screening Visit		
Assessment Name	Construct measure	Time to complete (min)
Phase One of In-Person Screening		
Beck Depression Inventory-II	Depression	10
Montreal Cognitive Assessment	Global cognitive function	10
Beck Anxiety Inventory	Anxiety	10
Starkstein Apathy Scale	Apathy	5
		Total time: 35 minutes
Phase Two of In-Person Screening		
Letter number sequencing	Attention/working memory	5
Stroop color word test		10
Wisconsin Card Sorting Test	Executive function	15
Trail making test		5
Action Fluency Test		1
Hopkins Verbal Learning Test-Revised	Memory	10
Brief Visuospatial Memory Test-Revised		10
Judgment of Line Orientation short version	Visuospatial	10
Hooper Visual Organization Test		15
Similarities test	Language	10
Boston Naming Test Short form		5
Theories of Cognitive Abilities	Expectation of cognitive change	3
Need for Cognition Scale	Enjoyment of cognitively challenging tasks	5
The Memory for Intentions Test	Prospective memory	15
Modified Fatigue Impact Scale	Fatigue	5
		Total Time: 124 minutes

Table 2. Guidelines from the Movement Disorder Society Task Force on Defining & Assessing MCI¹⁰	
Assessment:	
Level 1	Allows for diagnosis of possible PD-MCI using either a test to assess global cognitive function (i.e., the MoCA) or a limited battery of neuropsychological tests. Based on MoCA total scores, 26 or higher indicates PD-N, 21-25 indicates PD-MCI and less than 21 indicates PD-D ^{41,42} .
Level 2	Allows for diagnosis and subtyping of PD-MCI using a full battery of neuropsychological tests which should include at least two tests in each of the five domains most affected in PD.
Definition of impairment: Using neuropsychological tests and appropriate normative data; impairment is defined as 1 standard deviation below normative mean in 2 tests in the same domain or any two tests in different domains.	

Phase 3: Baseline data collection

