5.0 Data Analysis

All test administrators will undergo the same training. Data will be cleaned and tested for normality (if normality tests fail, appropriate transformations will be made), and proper missing data imputation techniques will be used. Test for multicollinearity will be made. The 3 treatment groups will be characterized using descriptive statistics for demographic factors, disease-related variables, and medication use. Groups will be examined for comparability according to the descriptive variables using ANCOVA and mixed-effects model with random subject effects. For ANCOVA, type I error rate ($\alpha=0.05$) will be adjusted for multiple comparisons using Bonferroni corrections.

Neuropsychological Data Analytical Approaches. For Aims 2 and 3, data will be analyzed using a two-level longitudinal mixed effects model with random subject effects to incorporate correlation of measurements nested within the same subject. Covariates will include medication dose, anxiety, apathy, and depression level. Parameters will be estimated using measurements from baseline, endpoint, and follow-up. The group by time interaction parameter will be used to examine the difference of the trends between the three groups. Significance of this parameter will indicate that treatment is efficacious in terms of EF over time when adjusted by covariates. To assess immediate effects of CCT, an experiment group contrast will be formed using test score means at baseline and endpoint and a control group contrast will be made with those same types of means. To assess sustainability of CCT effects, contrasts using means of test scores at endpoint and follow-up will be made for each group. Estimates of variance components from mixed-model analysis will be used to calculate test statistics. Data analysis will be performed using SAS 9.3 Proc Mixed. This modeling process will be reported for each outcome of interest in Aims 2 and 3. Potential moderators of the effects of the CCT will be explored through Pearson correlations and regression analyses. Factors include, age, age at PD onset, disease duration, MoCA score, depression, anxiety, apathy, L-dopa equivalent dose, PD-MCI subtype diagnosis,

scores on training perception, prior computer use and cognitive training. Co-morbidities and medications will be considered as confounders.

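### The moderator analysis names Pearson correlation and an unspecified regression but no factor-by-arm term, so it cannot separate moderators of the CCT effect from factors that predict change in every arm

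*Combined protocol and SAP*

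**What the plan says.** The relevant text is in 5.0 Data Analysis, under the neuropsychological analytical approaches. The method is given in one sentence: "Potential moderators of the effects of the CCT will be explored through Pearson correlations and regression analyses". The candidate list follows: "Factors include, age, age at PD onset, disease duration, MoCA score, depression, anxiety, apathy, L-dopa equivalent dose, PD-MCI subtype diagnosis", ending with "scores on training perception, prior computer use and cognitive training". That makes 11 or 12 factors, depending on whether the last two items count as one or two.

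For this step the plan does not name the dependent variable, the arms to be included, the terms of the regression or a multiplicity rule. Bonferroni is mentioned only for ANCOVA. The one interaction named belongs to the efficacy model: "The group by time interaction parameter will be used to examine the difference of the trends between the three groups". Medication dose, anxiety, apathy and depression enter that model as covariates, but none is crossed with group.

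Two further passages bear on the list. The plan states "Test for multicollinearity will be made", without saying what would follow from the result. The screening questionnaire (1.0 Study Design and Methods) collects "Parkinson's disease-related history (year of diagnosis, number of years on Parkinson's medication and side of motor symptom onset". A year of symptom onset is not listed.

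**The concern.** To ask whether a factor moderates the CCT effect is to ask whether the CCT-versus-control difference varies with that factor. A correlation of the factor with a score or a change score leaves the control arm out of the question, or pools it in without distinction. A factor that predicts change equally in trained and untrained Veterans will correlate just as well as a true moderator.

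The risk is a practical one here. The same battery is given at baseline, endpoint and follow-up (Table 3), so scores can rise with retesting in every arm, including the active control. Age or baseline MoCA could plausibly predict that rise whatever the arm, although the documents give no values.

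The pilot data are to support a larger grant proposal (3.0 Benefits of participation in the study). A prognostic factor mistaken for a moderator could misdirect the choices made there. The documents do not say that the next trial will select or stratify on these factors, so this is a possible consequence and not a planned one.

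**Working it through.** **Inputs from the documents.** Three arms of 15, 45 in total. Two arms receive CCT (2 × 15 = 30) and one receives CCT control (15). Alpha is 0.05, with sidedness not stated.

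**Assumptions.** Two-sided tests, no dropout, and a factor that correlates r with change equally in every arm, so that true moderation is zero. The documents give no r; 0.2 to 0.5 is shown. The plan states no power or error rate for this step, so there is no figure to reproduce.

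**Step 1: correlation in the 30 CCT Veterans (Fisher z).** Probability of significance ≈ Φ(atanh(r) × √(n − 3) − 1.96), with √27 = 5.196.

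- r = 0.3: 0.3095 × 5.196 = 1.608; Φ(−0.352) = 0.36
- r = 0.4: 0.4236 × 5.196 = 2.201; Φ(0.241) = 0.60
- r = 0.5: 0.5493 × 5.196 = 2.854; Φ(0.894) = 0.81

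**Step 2: simulation.** 5,000 trials per row, with a CCT effect of 0.5 SD on mean change. Entries are the percentage of trials with p < 0.05 when there is no moderation.

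| r | Pearson, all 45 | Pearson, 30 CCT | Pearson, one arm of 15 | Main-effect regression adjusted for arm | Factor-by-arm test |
|---|---|---|---|---|---|
| 0.2 | 24 | 18 | 11 | 24 | 5 |
| 0.3 | 51 | 37 | 19 | 52 | 4-5 |
| 0.4 | 76 | 60 | 32 | 77 | 6 |
| 0.5 | 94 | 83 | 50 | 94 | 4-5 |

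The last column covers the three-arm 2-df test and the 1-df test of CCT versus CCT control. The main-effect regression does no better than pooled Pearson, so regression helps only if the interaction is in it.

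**Step 3: when moderation is real.** Hold the CCT slope at 0.5 SD per SD and change the control slope.

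| Control slope | Slope difference | Pearson, all 45 | Pearson, 30 CCT | 1-df interaction |
|---|---|---|---|---|
| 0.5 | 0 | 94% | 83% | 4% |
| 0 | 0.5 | 63% | 82% | 39% |
| −0.5 | 1.0 | 21% | 83% | 90% |

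The CCT-only correlation is significant in 82-83% of trials whether moderation is absent, moderate or large, so it carries no information on the question. Pooled Pearson moves the wrong way: its hit rate falls as moderation grows. Only the interaction responds correctly.

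**Step 4: cost of isolating CCT.** Both CCT arms against the double-control arm gives a slope-difference variance proportional to 1/30 + 1/15 = 0.100. CCT+PRIIS control against CCT control+PRIIS control gives 1/15 + 1/15 = 0.133. The standard error is larger by √(0.133/0.100) ≈ 1.15, so power for a difference of 0.5 falls below 39%.

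**Step 5: age, age at onset and duration.** If duration = age − age at onset, a model with an intercept and all three has rank 3 of 4, and the three effects cannot be estimated together. If duration runs from diagnosis and onset from first symptoms, with an assumed lag of 0-3 years, the rank is 4. In one simulated sample (ages 50-85, durations 0-15 years, both assumed) the variance inflation factors were about 27 to 180.

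**The case against.** The strongest reply is that the plan names regression as well as correlation, and a product term in a regression is the ordinary way to test moderation. A reader might infer that the investigators chose correlation in place of an interaction. The text does not support that: the regression has no stated terms, so an interaction is neither planned nor excluded. What stands against the reply is that Pearson is itself a named method for this question, and a main-effect regression shares its fault.

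Other stronger readings also go too far:

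- That prognostic factors will be reported as moderators. The step is described as exploration of potential moderators, and no rule turns a significant correlation into a claim. It is a risk whose size depends on r.
- That the three age variables are exactly collinear and the model must fail. This needs a shared reference date, which the documents do not define, and all three factors in one model, which is not stated. It does not touch correlations taken one at a time, and a multicollinearity check is planned, though without a stated consequence.
- That Pearson is undefined for PD-MCI subtype. With two levels it is the point-biserial correlation; it loses meaning only with more than two unordered levels, and the coding is not given.
- That the number of factors is the fault. Twelve independent null tests give 1 − 0.95^12 = 46% chance of at least one hit, but twelve interaction tests would give the same, and the listed factors are not independent.

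It is also fair to say that the interaction test is weak at this size. That limits what a pilot of 45 can learn about moderation. It does not make an arm-free statistic a substitute.

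**Conclusion.** The concern holds in limited form. One named method cannot answer the question put to it, and the other is not specified well enough to show that it can. For a purely prognostic factor with r between 0.3 and 0.5, the false-lead rate is about 36-83% by Pearson in the CCT Veterans and 51-94% in all 45, against about 5% for an interaction test. These rates depend on the assumed r, two-sided testing at 0.05, equal slopes across arms and no dropout. At r = 0 every method gives about 5%, so the problem arises only for factors that do predict change.

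The analysis is exploratory and secondary, and the group-by-time efficacy comparison is unaffected. The change is nevertheless worth making because it is cheap and the results are meant to inform a larger proposal. The redundancy of the age variables is a minor adjunct: exact or near-exact according to the reference date, and relevant only if all three enter together.

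**What to change.** Replace the Pearson step in 5.0 Data Analysis with the following.

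1. For each baseline factor, one at a time, add factor-by-arm-by-time terms, with their lower-order terms, to the planned mixed model. Fit it on all 45 Veterans with arm kept at three levels, and report endpoint and follow-up.
2. Take the CCT moderation estimate from CCT+PRIIS control versus CCT control+PRIIS control. Any contrast pooling the two CCT arms is secondary, because it mixes in PRIIS.
3. Report each estimate with a 95% CI, labelled exploratory and not adjusted for multiplicity.
4. Enter PD-MCI subtype as a categorical factor.
5. Do not put age, age at onset and disease duration in one model together. State the reference date for the last two.
6. Training perception is collected at weeks 4 and 8, after randomisation. Report it as a descriptive association and not as a moderator.

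The cost is a paragraph of SAP wording and some extra runs of a model already planned. Intervals will be wide: power is about 39% for a slope difference of 0.5 SD per SD with the CCT arms pooled, and lower for the 15-versus-15 contrast. Fewer moderators will be claimed. The change does not remove multiplicity across factors, which is why the exploratory label is needed.

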Repeated measures/study outcomes are included in a standardized battery of test that will be repeated at baseline, endpoint and follow-up. The battery is expected to take approximately 130 minutes to complete.

Tests administered during screening (e.g., the BDI-II, MoCA, BAI, and HVLT, Memory for Intentions Test, and Modified Fatigue Impact Scale) will not be replicated at baseline, but are included in Table 3 below to indicate it is a repeated measure.

Table 3: Repeated Measures Assessment Tools used in the RCT			
Assessment Name (Abbreviation)	Outcome	Construct measure	Time to complete (min)
NIH-EXAMINER components:	1° (composite score of 7 tests listed below)	Executive function	29 total
Dot counting	2°	Working Memory	7
1-back			5
2-back			5
Flanker	2°	Cognitive Control	5
Set Shifting			5
Letter	2°	Verbal Fluency	1
Category			1
Hopkins Verbal Learning Test-Revised (HVLT)	2°	Memory	10
Symbol Digit Modalities Test (SDMT)	2°	Processing speed	5
The Memory for Intentions Test (MIST)	2°	Prospective memory	15
Monetary-Choice Questionnaire	2°	impulsivity	10
Parkinson's Disease-Cognitive Functional Rating Scale (PD-CFRS)	2°	Real-life function	5
The Activity Measure for Post-Acute Care™ (AM-PAC™) –Applied Cognition questionnaire	2°	Real-life function	10
Timed instrumental activities of daily living (iADL)	2°	Real-life function	15
Beck Depression Inventory-II	2°	Depression	10
Beck Anxiety Inventory	2°	Anxiety	10
Starkstein Apathy Scale	2°	Apathy	5
Montreal Cognitive Assessment	2°	Global Cognition	10
Epworth Sleepiness Scale	2°	Sleepiness	5
Modified Fatigue Impact Scale	2°	Fatigue	5
			Total Time: 144 minutes

Phase 4: Intervention

Participants will be randomized to one of three groups: CCT+PRIIS (n=15), CCT+PRIIS control (n=15) or CCT control +PRIIS control (n=15) and issued a VA iPad to take home and complete the study intervention.

Participants and researchers who are administering and scoring outcome measures will be blinded to group assignment. Effectiveness of blinding will be evaluated by using data collected from mid-point and endpoint questionnaires that assess perception of training intervention⁶⁹. The PI will oversee the RCT and coordinate research procedures and thus will not be blinded to treatment assignments. [name], who will be blinded to group assignments, will coordinate sensitive aspects of the study that require blinding.

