CCT training games are developed by Posit Science Corporation, San Francisco, CA, and are designed to train components of EF specifically affected in PD (Table 5). Participants will be asked to complete, at home, 4 sessions/week for 8 weeks. Each session will take 30min; totaling 16hr of CCT training. No dose effect is established for CCT, thus we looked to the literature^{24,28} and expertise of consultants at Posit Science for guidance on the dose, and determined that 16 hours may be sufficient to detect effects of training on cognition. Progress of the training will not be fixed; training modules will be continuously adaptive, following "staircase" procedures⁷⁰, assuring that success in training on ~75% of exercise trials. While this leads to a

different progression of training across participants, it provides a customized, challenging and internally rewarding training experience that should increase performance motivation and optimize learning⁷¹. CCT active control will include 9 entertaining online games that are played on the same platform as the CCT games (Fig 2). Veterans will be asked to complete, at home, 4 sessions/week for 8wk.

For PRIIS, participants will work with a study team member to determine patient-centered prospective memory tasks. Participants will collaboratively agree on problem areas/areas that they would like to manage better (i.e., remember when to take my medicine) formulated in the form of up to three personal rehabilitation goals using the Bangor Goal-Setting Interview (BGSI)⁷². They will rate their own performance on these goals at initial and follow-up assessments. Participants will be taught to form a 'When X, I will do Y', recite the statement aloud three times, and imaging themselves performing the task during the situation in accordance with the statement for 30 s. In addition to the three patient-centered goals, a common goal for all participants in each group will be completing weekly CCT/CCT active control assignments (e.g., on Monday, Wednesday, and Friday, when I eat lunch, I will complete my cognitive training games).

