PRIIS active control will include verbal rehearsal. These participants will be instructed to recite their prospective memory task (complete weekly intervention assignments) at least three times a day and study them for 30 s. Everyone will be given a handout with strategy instructions as reference. Weekly calls will be made to participants to assess their progress with the prospective memory task of completing weekly intervention assignments. Barriers, facilitators, and resources will be noted and discussed.

The study team member designated as the cognitive coach will make weekly phone calls to the participant to assess compliance and help troubleshoot any difficulties with the assigned programs. During the call, the cognitive coach will help the participant assess their progress with the prospective memory task of completing weekly intervention assignments (and for PRIIS the other goals). Barriers, facilitators, and resources will be discussed.

At midpoint and endpoint (weeks 4 and 8 of the intervention), participant's perception of the training will be assessed, over the phone and by a study team member, with a short questionnaire that will include questions such as: Are the games enjoyable? Are the games challenging? Do you look forward to playing the games? Are you motivated to play the games? Do you think your cognition is improving because of the games? Answers will be rated on a Likert scale. All participants will be reassessed with the neuropsychological battery at endpoint and one month after endpoint. During the one month after endpoint, participants will not be contacted during the one month except to remind them of their appointment for the follow-up assessment.

Specific to the CCT intervention, several factors may contribute to non-compliance with program use. Several elements of flexibility will be incorporated in the treatment schedule to accommodate the challenges that Veterans with PD may encounter. First, the participant may require extra time to complete the program. Participants will be asked to engage in four 30-minute sessions per week for 8 weeks, which is 16 hours in total.

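### Training-perception scores exist only after randomisation and can result from improvement itself, so they should not be listed as a potential moderator of the CCT effect

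*Combined protocol and SAP*

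**What the plan says.** Section 5.0 (Data Analysis) states: "Potential moderators of the effects of the CCT will be explored through Pearson correlations and regression analyses". The factors it then names are mostly patient characteristics such as age, disease duration and cognitive subtype. The list closes with "scores on training perception, prior computer use and cognitive training". It does not restrict factors to values obtained before randomisation, and it does not say whether the regressions contain a factor-by-group term.

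Section 1.0, Phase 4, gives the timing of the perception questionnaire: "At midpoint and endpoint (weeks 4 and 8 of the intervention". The example items cover enjoyment, challenge, looking forward to play and motivation, and one asks: "Do you think your cognition is improving because of the games". Phase 5 adds a semi-structured interview at the endpoint visit, which also covers how the training was perceived.

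The same questionnaires have a second use in Phase 4: "Effectiveness of blinding will be evaluated by using data collected from mid-point and endpoint questionnaires that assess perception of training intervention".

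Table 1 (Phase 2, screening) contains two related scales given before randomisation: Theories of Cognitive Abilities, for "Expectation of cognitive change", and the Need for Cognition Scale, for "Enjoyment of cognitively challenging tasks". Section 5.0 does not name either of them.

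**The concern.** A moderator analysis asks for whom a treatment works. It can be read that way only if the factor is not itself changed by the treatment or by the outcome. A perception score taken during and after training does not meet that condition. A participant whose EF improves may notice it and say so, and the score rises because of the outcome. A correlation with EF change could then be reported as CCT working better in people who enjoy it or believe in it, when every participant had the same effect.

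Section 3.0 says the pilot data will support a larger grant proposal. A mistaken statement about who benefits could be carried into it, although the documents do not say that moderator results will shape that proposal.

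**Working it through.** **1. Timing of the listed factors**

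| Factor in section 5.0 | When obtained (section 1.0) | Value before randomisation? |
|---|---|---|
| Age, onset, duration, subtype, prior computer use and cognitive training | Screening | Yes |
| MoCA, depression, anxiety, apathy | Screening, then repeated (Table 3) | Yes |
| Training perception | Weeks 4 and 8; endpoint interview | None |

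For the repeated scales, an analyst can choose the screening value. For training perception no choice of visit helps.

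**2. Routes by which the score can be affected**

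- *Outcome to score.* The item "Do you think your cognition is improving because of the games" asks participants to judge their own benefit. Relating that answer to EF change relates improvement to perceived improvement.
- *Arm to score.* Phase 4 describes CCT as a "challenging and internally rewarding training experience that should increase performance motivation", and the questionnaire asks about challenge and motivation. Control participants play different games, so answers can differ by arm. The control games are also described as entertaining, so the direction of any difference in enjoyment is unclear.

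**3. Illustration of size**

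The plan contains no figure on this point to reproduce. From the documents: 3 arms of 15, so 2 × 15 = 30 with CCT and 15 without. Everything else is assumed: complete data, two-sided 0.05, and an identical CCT effect for everyone, so there is no moderator to find.

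Model 1 (20,000 trials per cell):
- EF change = 0.5 × CCT + noise, with noise SD = √(2 × (1 − 0.7)) = 0.775 for an assumed within-subject correlation of 0.7.
- Score = r × standardised own change + √(1 − r²) × noise.
- Test A: Pearson correlation in the 30 CCT participants. With 28 degrees of freedom the critical |r| is 0.361.
- Test B: CCT-by-score term in a regression on all 45.
- The largest Monte Carlo standard error is √(0.25/20,000) = 0.35 percentage points.

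| Chance of p<0.05 | r=0 | 0.2 | 0.3 | 0.4 | 0.5 |
|---|---|---|---|---|---|
| A, same r in all arms | 5% | 19% | 37% | 61% | 82% |
| B, same r in all arms | 5% | 5% | 5% | 5% | 5% |
| B, r in CCT arms only | 5% | 10% | 15% | 25% | 37% |

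Model 2 (10,000 trials per setting): score = a × CCT + b × EF change + noise, unit SDs, CCT effect d from 0 to 0.8 SD.
- The within-arm correlation is b/√(1 + b²): b = 0.3 gives 0.3/√1.09 = 0.29, and b = 0.5 gives 0.5/√1.25 = 0.45.
- With b = 0.3 to 0.5 in both arms and a = 0, the CCT-only correlation is significant in 34% to 72% of trials. This agrees with row A once b is converted to r. The correlation pooled over all 45 is significant in 48% to 92%.
- If the score depends on arm alone (b = 0, a = 0.5 to 1, d = 0.5 to 0.8), the pooled correlation is significant in 6% to 17%, and the CCT-only correlation and the interaction test stay near 5%.
- The interaction test is significant in 26% to 27% if b = 0.5 in the CCT arms and 0 in control.

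In these settings the route from outcome to score matters much more than the route from arm to score.

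**The case against.** The strongest reply is that this is one of about a dozen factors to be explored in a pilot of 45, and that no primary test, sample size or decision rule depends on it. That stands, and it limits the weight of the point. It does not remove it: calling an analysis exploratory answers multiplicity and low power, not a factor that the outcome can cause.

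A second reply is that the percentages are simply the power of a correlation test at an assumed r, and that section 5.0 does not say the correlation would be run among CCT participants only. Both are true. The documents give no value for r, and measurement error in the score would lower it.

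A third reply is that regression is also planned, and that a CCT-by-score term keeps its 5% error rate if perception follows change equally in all arms. This stands in part. Section 5.0 neither specifies nor excludes such a term, and the term fails if CCT participants notice change more than controls do.

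A fourth is that the factor list in section 5.0 need not be exhaustive, so leaving the two screening scales unnamed is not an error. That is accepted; adding them is optional.

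A reader might also infer from the blinding check that the plan expects answers to differ by arm. It shows only that the answers will be examined for this.

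**Conclusion.** The point holds, as a minor one. Training perception has no value before randomisation, and one of its items asks about improvement directly, so an association with EF change cannot be read as moderation. This conclusion rests on the text alone and does not depend on any simulated value. The percentages show what could happen under assumed correlations and a constant CCT effect.

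Three stronger readings are tempting, and the documents support none of them:

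- *The EF efficacy result is compromised.* Training perception is not among the covariates of the mixed model, so the group-by-time test is untouched.
- *A false moderator should be expected at the simulated rates.* Nothing in the documents says how closely perception will follow EF change.
- *The same fault applies to MoCA, depression, anxiety and apathy.* They are repeated after randomisation, but each has a screening value that can be used.

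**What to change.** In section 5.0, remove training perception from the list of potential moderators. State that it is kept for the blinding check and that any link with EF change will be reported only as a post-randomisation association.

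If expectation or enjoyment is of interest as a moderator, name the Theories of Cognitive Abilities and Need for Cognition scores from screening, test each with a factor-by-group term on EF change, and label the results hypothesis-generating. These scales measure general dispositions, not opinions of these particular games, so they replace the question rather than the score.

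The cost is a few sentences before analysis and no new data. The downside is low power: in Model 1, a slope difference equivalent to r = 0.5 in the CCT arms against 0 in control was detected in only 37% of trials of 45, so most such tests would be inconclusive.
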